7.2 Primary Analysis

The primary analysis will be conducted when target enrollment is complete, and each subject had the opportunity to complete 6 months on study or withdraws from study.

[figure not shown]
7.3 Final Analysis

The final analysis will be conducted after all cohorts and dose-expansion subjects have ended the study. Primary and final analysis may be combined in case all subjects have ended study close to the time point of the primary analysis.

8. Data Screening and Acceptance

8.1 General Principles

The objective of the data screening is to assess the quantity, quality, and statistical characteristics of the data relative to the requirements of the planned analyses.

8.4 Detection of Bias

Lack of protocol compliance and the potential for biased statistical analyses will be examined by assessing the incidence of important protocol deviations in each cohort. The clinical study team will identify and document the criteria for important protocol deviations.

8.5 Outliers

Outliers will not be excluded unless scientifically justified. Pharmacokinetic (PK) serum concentration data will be evaluated for outliers by visual inspection, and decisions to re-assay individual samples will be made in accordance with standard PK evaluation practice.

8.6 Distributional Characteristics

Where appropriate, the assumptions underlying the proposed statistical methodologies will be assessed. If required data transformations or alternative non-parametric methods of analyses will be utilized.

8.7 Validation of Statistical Analyses

Programs will be developed and maintained and output will be verified in accordance with current risk-based quality control procedures. Tables, figures, and listings will be produced with validated standard macro programs where standard macros can produce the specified outputs.

The production environment for statistical analyses consists of Amgen-supported versions of statistical analysis software; for example, the SAS System version 9.4 or later.

9. Statistical Methods of Analysis

9.1 General Considerations

Descriptive statistics will be provided for selected demographics, safety, PK, pharmacodynamics [REDACTED] data by dose cohort or time as appropriate. Unless otherwise stated, the data analysis will be conducted using subjects in the Safety analysis set. Subjects in the dose escalation part of the analysis will be summarized by each AMG 404 dose level.

Descriptive statistics on continuous data will include means, medians, standard deviations and ranges, while categorical data will be summarized using frequency counts and percentages. Graphical summaries of the data may also be presented. When data are summarized by time, the values recorded against the scheduled time points listed in the protocol will be used. When assessing minimum/maximum increases or decreases over the study, all assessments, including unscheduled assessments will be used. Data listings will include all available data from all enrolled subjects unless specified otherwise.

All descriptive statistics and graphical summaries may be presented separately for Cohort 5, [REDACTED] versus all the other cohorts. Similarly, all the efficacy and the safety analyses may be conducted separately for Cohort 5, [REDACTED] versus all the other cohorts.

Efficacy endpoints will be summarized separately for Cohort 7, Cohort 8, Cohort 9, [REDACTED].

Confidence intervals (CI) for proportions will be estimated using an exact method proposed by Clopper-Person ([Clopper & Pearson, 1934](#)). Kaplan-Meier methods will be used to estimate the median and percentiles for time to event endpoints with CI calculated using the Brookmeyer and Crowley method ([Brookmeyer & Crowley, 1982](#)). Kaplan-Meier methods will be used to estimate landmarks for time to event endpoints (eg, 1-year OS) with the Greenwood formula ([Kalbfleisch & Prentice, 1980](#)) used to estimate the standard error used in CI calculation.

9.2 Subject Accountability

A summary of subject disposition and investigational product disposition will be provided for all subjects enrolled in the study ie, the number and percent of subjects who were enrolled, received investigational product, discontinued from investigational product (including reasons for discontinuing), completed study, discontinued the study (including reasons for discontinuing) will be summarized by cohort.

Key study dates for the first subject enrolled, last subject enrolled, and last subject's end of study will be presented.

9.3 Important Protocol Deviations

Important Protocol Deviations (IPDs) categories are defined by the study team before the first subject's initial visit and updated during the IPD reviews throughout the study prior to database lock. These definitions of IPD categories, subcategory codes, and

descriptions will be used during the course of the study. The final IPD list is used to produce the Summary of IPDs table and the List of Subjects with IPDs. In addition, a separate listing of all inclusion and exclusion deviations will be provided.

A protocol deviation of listing of subjects impacted due to COVID-19 will also be provided.

9.4 Demographic and Baseline Characteristics

Demographic characteristics including age, age groups (18 to 65, 66 and above), sex, race, ethnicity and baseline characteristics, which may include height, weight, Eastern Cooperative Oncology Group (ECOG) performance status, baseline disease stage, number of prior anti-cancer therapies, cancer-related surgery and primary tumor type will be summarized using descriptive statistics.

If multiple races have been reported for a subject, the subject will be categorized as multiple.

9.5 Efficacy Analyses

In general, the analysis of efficacy endpoints will be based on the Safety Analysis Set unless otherwise specified.

9.5.1 Analyses of Primary Efficacy Endpoint(s)

No efficacy parameter is considered in primary endpoints.

9.5.2 Analyses of Secondary Efficacy Endpoint(s)

For all subjects treated at the RP2D and separately by cohort, the following analyses will be done. The proportion of subjects with confirmed objective tumor response (partial and complete response) and disease control rate (DCR) (partial or complete control) with corresponding exact 80% CI will be calculated and tabulated. Similarly, the proportion of subjects and 80% CI will be tabulated for 1-year duration of overall response, 1-year PFS, 1-year duration of stable disease and 1-year OS. Kaplan-Meier curve will be presented for duration of overall response, PFS, OS and duration of stable disease with estimates for rate and 80% CI at selected weeks based on the Brookmeyer and Crowley method ([Brookmeyer & Crowley, 1982](#)) if data allows.

9.5.3 Analyses of Exploratory Efficacy Endpoint(s)

No efficacy parameter is considered in exploratory endpoints.

9.6 Safety Analyses

9.6.1 Analyses of Primary Safety Endpoint(s)

Unless otherwise specified, statistical analyses on safety endpoints will be done using subjects from the safety analysis set, which includes subjects that are enrolled and received at least 1 dose of AMG 404.

The analysis of the subject incidence of dose limiting toxicities (DLT) will be based on the DLT evaluable set defined in [Section 6.2](#). A summary of the subject incidence of dose limiting toxicities (DLT) with corresponding 95% CI will be provided.

9.6.2 Adverse Events

The most current version of the Medical Dictionary for Regulatory Activities (MedDRA) will be used to code all adverse events to a system organ class and a preferred term. The identification of adverse events of special interest is a continuous process. Events may be identified and documented as the safety profile of the drug is characterized. The severity of each adverse event will be graded using CTCAE version 5.0.

Tables will be provided for Subject incidence of all treatment-emergent, serious, treatment-related, those leading to withdrawal of investigational product, events of special interests and fatal adverse events by system organ class and preferred term in descending order of frequency. Where appropriate the tables will also be presented by worst grade.

Details of each treatment-emergent adverse event will be listed. Listings and/or narratives of any on-study deaths, serious treatment-emergent adverse, and grade 3 or higher treatment-related adverse, including adverse events leading to discontinuation of AMG 404, also will be provided should they occur.

9.6.3 Laboratory Test Results

Laboratory data will be summarized using standard descriptive statistics at each scheduled time point in the study. For continuous parameters, a summary of the changes from baseline to each post dose laboratory assessment will also be produced. Shifts in selected laboratory parameters between baseline and the worst on-study value will be summarized according to the NCI CTCAE toxicity grades. Safety Laboratory collection includes chemistry, hematology, pregnancy test (for women of childbearing potential) either urine or serum. The parameters described in Table 13-1 of the protocol will be collected, converted to Amgen standard units.

Selected individual analytes will be summarized by cohort using standard descriptive statistics at each of the scheduled time points through the study up to the safety follow-up visit. For continuous parameters, a summary of the changes from baseline to each

post dose laboratory assessment will be produced for each cohort. Tables of shifts from baseline to the worst-case on-study increased and decreased values (graded according to the NCI Common Toxicity Grading Criteria) will be provided for selected laboratory parameters with available NCI-CTCAE grades. Unscheduled assessments will be included in the shift tables.

Subject incidence of suspected Hy's law cases (Hy's law predicts potential for drug-related hepatotoxicity) will be summarized by cohort. A listing of alanine aminotransferase, aspartate aminotransferase, alkaline phosphatase, and total bilirubin values at each time point may be produced for the subjects suspected of Hy's law case.

Boxplots may be plotted by time point and cohort for selected analytes.

Urine analysis

Blood, protein and glucose will be graded in the following manner: 0='0 or Trace', 1='1+', 2='2+', 3='3+', 4='4+'. Microscopic parameters (WBC, RBC, epithelial cells, bacteria, casts, crystals) will be graded in the following manner: 0='0-4 none, rare, occasional', 1='5-50 moderate, few', 2='>50 many, heavy, too numerous to count'. Data recorded as "Present" will not be included in the summary.

The number and percent of subjects with a worst post-dose presence of blood in the urine of '0 or Trace', '1+', '2+', '3+', or '4+' will be presented (also for protein and glucose in the urine).

Depending on the size and scope of changes in urinalysis data, summaries over time and/or changes from baseline over time may also be provided. Unscheduled assessments will be included in the analysis.

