#### 11.4.2.3.3 Laboratory Test Results

Clinical chemistry, hematology, and urinalysis data will be **summarized**. Depending on the size and scope of changes in laboratory data, summaries of laboratory data over time and/or changes from baseline over time may be provided. Tables of maximum shifts from baseline for selected laboratory values may also be provided.

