2.1 Objectives and Endpoints

Objectives	Endpoints
Primary	

To evaluate the safety and tolerability and determine the recommended phase 2 dose (RP2D) of AMG 404 in patients with advanced solid tumors	
Dose limiting toxicities (DLTs), treatment-emergent adverse events, treatment-related adverse events, and changes in vital signs, and clinical laboratory tests
Secondary	

To evaluate the pharmacokinetics (PK) of AMG 404, as a monotherapy [REDACTED]	
PK parameters of AMG 404 including, but not limited to, maximum observed serum concentration (C_{max}), time to achieve C_{max} (t_{max}), and area under the serum concentration-time curve (AUC)

To assess the immunogenicity of AMG 404, as a monotherapy [REDACTED]	
Subject incidence of anti-AMG 404 antibodies

To evaluate the preliminary antitumor activity of AMG 404, as a monotherapy [REDACTED]	
Objective tumor response, duration of overall response, progression-free survival, disease control rate (DCR), and duration of stable disease measured by CT/MRI and assessed per modified RECIST 1.1

Exploratory

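### SAP 9.6.3 leaves urinalysis results recorded as 'Present' out of the summary but keeps negatives as grade 0, so detected but unquantified findings drop out of the reported counts (minor)

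*SAP*

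**What the plan says.** The urine analysis part of SAP 9.6.3 has three elements that bear on this point.

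- **Scales.** Blood, protein and glucose run from grade 0 (nil or trace) to grade 4 (4+). The microscopic parameters (WBC, RBC, epithelial cells, bacteria, casts, crystals) have three levels: "0='0-4 none, rare, occasional', 1='5-50 moderate, few', 2='>50 many, heavy, too numerous to count". Negative results are therefore kept and graded 0, together with trace, rare and occasional findings.
- **Exclusion.** Directly after the microscopy scale, the SAP states that data recorded as 'Present' "will not be included in the summary". No reason is given. There is no category for these results, no count of them and no sensitivity summary.
- **Table.** The SAP then commits to "The number and percent of subjects with a worst post-dose presence of blood in the urine" at each dipstick level, and the same for protein and glucose. Other urinalysis summaries are optional.

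SAP 2.1 places laboratory tests in the primary endpoint: "treatment-related adverse events, and changes in vital signs, and clinical laboratory tests". Protocol 11.4.2.3.3 ("Clinical chemistry, hematology, and urinalysis data will be" summarized) covers urinalysis and states no exclusion. SAP 9.1 adds that "Data listings will include all available data from all enrolled subjects unless specified otherwise".

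**The concern.** Whether a record is left out depends on its value. A negative result counts in the table. A finding that was detected but not quantified does not, and the reader of the table is not told how many such findings there were.

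The setting makes such records plausible. Urinalysis is done at local laboratories (Protocol 10.2.4 and Table 13-1), at approximately 35 sites in many countries (Protocol 6.2.2), and the SAP sentence itself expects 'Present' to occur. Nephritis and renal dysfunction is a named class effect (Protocol Table 4-2). Laboratory abnormalities that the investigator judges not clinically significant are in general not recorded as adverse events (Protocol 10.2.4), so for those findings the laboratory summary is the main aggregate display. SAP 8.5 asks for scientific justification before an outlier is excluded; this exclusion has none.

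At stake is whether the urinalysis percentages by cohort can be taken at face value.

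**Working it through.** The documents state no figure on this point, so there is none to reproduce. The check is on direction first, then on size under stated assumptions.

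**Inputs (all assumed; the documents give none of them)**

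- p = true share of subjects whose worst post-dose grade is 1 or more.
- q = share of those subjects whose only positive record is 'Present'.
- s = share of truly grade-0 subjects recorded only as 'Present'.

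A subject with another graded result at least as high is unaffected.

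**Formulas**

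- Affected subjects stay in the denominator through other grade-0 results: reported rate = p(1 - q).
- Affected subjects leave the table: reported rate = p(1 - q) / (1 - pq - (1 - p)s).

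**Direction**

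- The numerator is p(1 - q) in both cases, which never exceeds p.
- If subjects stay in the denominator, the rate is below p whenever q > 0.
- If subjects leave the table, the rate is below p when 1 - q < 1 - pq - (1 - p)s. This reduces to q(1 - p) > s(1 - p), that is, q > s.

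**Size with s = 0** (left: subjects stay; right: subjects leave)

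| p | q = 10% | q = 25% | q = 50% |
|---|---|---|---|
| 10% | 9.0-9.1% | 7.5-7.7% | 5.0-5.3% |
| 20% | 18.0-18.4% | 15.0-15.8% | 10.0-11.1% |
| 30% | 27.0-27.8% | 22.5-24.3% | 15.0-17.6% |

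For p = 20% and q = 25%: 0.20 × 0.75 = 0.150, and 0.150 / (1 - 0.05) = 0.158.

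**Size with s > 0, subjects leaving the table, p = 20%**

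- q = 25%, s = 5%: 0.150 / (1 - 0.05 - 0.04) = 16.5%.
- q = 25%, s = 25%: 0.150 / (1 - 0.05 - 0.20) = 20.0%, no bias.
- q = 10%, s = 25%: 0.180 / (1 - 0.02 - 0.20) = 23.1%, bias reversed.

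**Illustration in a cohort of 40** (the planned size of Cohorts 7, 8 and 9). Suppose 8 subjects are truly positive (20.0%), 2 of them recorded positive only as 'Present'. The table shows 6/40 (15.0%) or 6/38 (15.8%). With a separate row and all 40 kept, it shows 6/40 (15.0%) with a graded positive and 2/40 (5.0%) unquantified, which together recover 8/40.

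**The case against.** The case against giving this weight is substantial, and most of it stands.

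- **Scope.** The sentence follows the microscopy scale and can be read as covering microscopy only. The committed worst-value table covers only blood, protein and glucose. On the narrow reading that table is untouched, and the exclusion affects only optional summaries.
- **Meaning of 'Present'.** A reader might infer that the rule removes only abnormal results and so always biases the rate downward. The SAP's own scales do not support this: trace, rare and occasional findings are detected yet graded 0. Only the effect on the count is certain; the effect on the rate depends on q, s and the denominator.
- **Zero rates.** A reader might also infer that the rate falls to zero at sites reporting only present or absent. That needs such sites to exist and 'absent' to be mapped to grade 0; the documents establish neither.
- **Repeat testing.** Urinalysis is scheduled at each cycle, at end of treatment and at safety follow-up (Protocol Table 3-1), and unscheduled results count (SAP 9.6.3). This makes it less likely that 'Present' is a subject's only positive record, so q may be small.
- **Consequence.** A hidden renal signal is not supported either. Protocol Table 13-2 grades nephritis by serum creatinine, which is in the chemistry panel, and SAP 9.6.3 plans change-from-baseline summaries and shift tables for selected laboratory parameters. Abnormalities judged clinically significant are adverse events (Protocol 13.5). The expansion stopping boundaries use treatment-related adverse events of grade 4 or higher (SAP 7.1).

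None of this supplies a reason for the exclusion or a count of what it removes. Listings keep the values, but they do not correct a tabulated percentage.

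**Conclusion.** The point holds, at minor severity. As written, the SAP keeps negative urinalysis results and leaves out detected but unquantified ones. This can lower, and can never raise, the number of subjects shown with a positive result. The reported rate falls whenever some positive subjects have 'Present' as their only positive record, except where affected subjects leave the table and 'Present' is at least as common among grade-0 subjects as among positives.

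The size is unknown. On an assumed true rate of 20% with no grade-0 subject recorded only as 'Present', the shortfall runs from about 2 percentage points (q = 10%) to 9-10 points (q = 50%). For the committed table it also depends on the sentence reaching blood, protein and glucose, which the text leaves open.

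Laboratory tests do belong to the primary endpoint, but urinalysis is one descriptive part of it. No test, dose decision rule or stopping boundary rests on this table, so it would be wrong to conclude that the primary safety assessment as a whole is biased.

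**What to change.** In SAP 9.6.3, replace the exclusion with a rule along these lines:

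- Add a 'Present, not quantified' row for every urinalysis parameter summarized, dipstick or microscopic. This also settles the scope question.
- Place a subject in that row when there is a 'Present' record and no graded positive result.
- Keep those subjects in the denominator, and show the number of such records by cohort.
- Do not assign 'Present' a grade in the main table.

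Counting 'Present' as the lowest positive grade may be added as a sensitivity line, labelled as possibly overstating abnormality. With p = 20%, q = 25% and s = 5%, that line would show 15% + 5% + 4% = 24% against a true 20%.

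The cost is one SAP sentence, one table row per parameter and a count. No new data are needed, since the values are already held for the listings.

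### SAP 9.6.3 commits to a worst post-dose urine grade table with no baseline reference and leaves urinalysis change from baseline optional, so persistent pre-dose findings cannot be told from new or worsened ones

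*SAP*

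**What the plan says.** SAP 2.1 and protocol 5.1 put "treatment-related adverse events, and changes in vital signs, and clinical laboratory tests" among the primary endpoints. Protocol Table 13-1 (Appendix 2) lists urine blood, protein and glucose as clinical laboratory tests.

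SAP 9.6.3 has a general part and a urinalysis part.

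- **General part.** It opens with "Laboratory data will be summarized using standard descriptive statistics at each scheduled time point in the study". It commits to change-from-baseline summaries for continuous parameters. It also commits to baseline-to-worst shift tables, which "will be provided for selected laboratory parameters with available NCI-CTCAE grades".
- **Urinalysis part.** It sets its own scale from 0 to 4 ("Blood, protein and glucose will be graded in the following manner"). It then commits to "The number and percent of subjects with a worst post-dose presence of blood in the urine of" each category, and the same for protein and glucose. Its closing lines say that, depending on the size and scope of changes, "summaries over time and/or changes from baseline over time may also be provided".

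Protocol 11.4.2.3.3 commits to summarizing urinalysis and leaves over-time, change-from-baseline and shift displays optional for all laboratory data.

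A baseline value will normally exist. Protocol Table 3-1 schedules urinalysis at screening and before the first dose, and SAP section 5 defines baseline as the last non-missing assessment before first AMG 404.

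**The concern.** The endpoint is change, but the one urinalysis display that is clearly promised describes level after dosing. Take three subjects: one at 2+ at baseline and throughout, one who goes from 0 to 2+, and one who improves from 3+ to 1+. The table records them as 2+, 2+ and 1+. The first did not change, the second worsened and the third improved, and the display cannot show this.

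The study is single-arm, so there is no concurrent group from which to judge background findings. Each subject's own baseline is the natural reference. What is at stake is how one descriptive safety table can be interpreted.

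**Working it through.** **1. Text comparison.** The plan states no figure on this point, so there is none to reproduce. The relevant outputs are:

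| Output in SAP 9.6.3 | Committed? | Within-subject baseline link for urine blood, protein, glucose? |
|---|---|---|
| Descriptive statistics by scheduled visit | Yes, for laboratory data in general | No. Frequencies by visit do not pair a worst value with that subject's baseline |
| Change from baseline | Yes, for continuous parameters | No. These results are graded categories |
| Shift from baseline to worst | Yes, for selected parameters with CTCAE grades | Not clearly. These analytes have a separate SAP scale |
| Worst post-dose urine grade | Yes | No |
| Urinalysis change from baseline over time | Optional | Possible, but not promised |

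**2. Simple illustration with assumed rates.** Let b be the proportion with a finding of 1+ or more before dosing that persists, and q the new-onset proportion among the rest. The table shows b + (1 − b)q, and the pre-existing share is b / [b + (1 − b)q]. With b = 0.10 and q = 0.05, the table shows 0.10 + 0.90 × 0.05 = 0.145, and the pre-existing share is 0.10 / 0.145 = 69%. Over b from 5% to 30% and q from 5% to 10%, that share runs from 34% to 90%. With q = 0, the table would still show on average 1 to 6 of 20 subjects, or 2 to 12 of 40 (n × b).

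**3. Illustration with fluctuating findings and no drug effect.** Here urine status varies between visits. Assume prevalence p of 1+ or more at any visit, a latent normal variable with within-subject correlation r, and k post-dose samples. Given a standard normal subject effect u, the chance of a positive sample is π(u) = Φ[(√r·u − c)/√(1 − r)], with c the upper-p normal quantile.

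- Worst post-dose positive: E[1 − (1 − π)^k].
- Also positive at baseline: E[π{1 − (1 − π)^k}].

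Simulation of 400,000 subjects gave the values below. Numerical integration of the two formulas agrees to within 0.002.

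| p | r | k | Worst 1+ or more | Positive at baseline | Negative at baseline (difference) | Negative share of those counted |
|---|---|---|---|---|---|---|
| 0.10 | 0.5 | 3 | 0.218 | 0.059 | 0.159 | 73% |
| 0.10 | 0.5 | 6 | 0.320 | 0.075 | 0.245 | 77% |
| 0.10 | 0.8 | 3 | 0.173 | 0.080 | 0.093 | 54% |
| 0.10 | 0.8 | 6 | 0.223 | 0.089 | 0.134 | 60% |
| 0.20 | 0.5 | 3 | 0.388 | 0.144 | 0.244 | 63% |
| 0.20 | 0.5 | 6 | 0.523 | 0.171 | 0.352 | 67% |
| 0.20 | 0.8 | 3 | 0.315 | 0.170 | 0.145 | 46% |
| 0.20 | 0.8 | 6 | 0.386 | 0.185 | 0.201 | 52% |

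The pre-existing share is the complement of the last column: 23% to 54%. In a cohort of 40 with p = 0.10, r = 0.8 and k = 3, about 40 × 0.173 = 7 subjects are counted, of whom about 40 × 0.080 = 3 were positive at baseline.

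The table also shows the limit of any baseline comparison. With no drug effect, 9% to 35% of all subjects are negative at baseline and positive at least once afterwards. A count of subjects who exceed baseline would still include them.

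**The case against.** The strongest reply is that the SAP does provide for baseline comparison. The closing lines of the urinalysis text allow change-from-baseline summaries, so a shift table could be produced without amending the plan. This matches protocol 11.4.2.3.3, and SAP 9.6.4 uses the same discretionary wording for vital signs, which belong to the same primary endpoint. That stands: the gap is an optional display that should be a committed one.

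A reader might infer more in four ways, and the documents do not support any of them.

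- **That the worst post-dose table is the only urinalysis output.** The opening sentence of SAP 9.6.3 speaks of laboratory data generally, and the section refers to Table 13-1, which includes urinalysis. By-visit summaries may therefore be intended. The later optional wording for urinalysis points the other way, so the text is ambiguous. On either reading, no within-subject link is promised.
- **That pre-existing findings are reported as treatment-emergent.** The table is labelled post-dose, which is accurate. A pre-dose finding that clears is not counted.
- **That a renal safety signal would be missed or invented.** Protocol Table 13-2 grades nephritis and renal dysfunction by serum creatinine, with dialysis at grade 4. Creatinine is a continuous chemistry parameter with committed change-from-baseline summaries. Protocol 10.2.4 also asks investigators to judge abnormal values against the subject's baseline and to record clinically relevant changes as events.
- **That most of the tabulated findings would be pre-existing.** That holds if baseline findings persist at rates such as b = 0.10 with q = 0.05. In seven of the eight fluctuating scenarios, more than half of the counted subjects were negative at baseline.

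**Conclusion.** The point holds as a low-cost improvement to a descriptive table. For urine blood, protein and glucose, no output clearly committed to in SAP 9.6.3 relates a subject's worst post-dose grade to that subject's baseline, although the endpoint is change. Persistent pre-dose abnormalities therefore cannot be separated from new or worsened ones in the display that will certainly be produced.

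The size is unknown. Every percentage above rests on assumed prevalence, correlation, persistence or number of samples, and none of these is in the documents. Consequences are limited: the stopping boundaries in SAP 7.1 use grade 4 or higher treatment-related adverse events, and no dose-limiting toxicity criterion in protocol 8.4.2 refers to the SAP urine grades.

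**What to change.** In SAP 9.6.3, keep the worst post-dose table and add one commitment: a shift table of baseline grade by worst post-dose grade for urine blood, protein and glucose, by cohort, with a row for missing baseline. Use the grading scale and the baseline definition already in the SAP. Report the number and percent of subjects whose worst post-dose grade exceeds baseline, among those with a baseline and at least one post-dose result.

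Adding the table is better than replacing the planned one, because subjects without a baseline result then stay in the existing display.

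The cost is one SAP sentence and one extra table, with no new data. Subjects without a baseline result drop out of the worsening percentage. A footnote should say that the worst of several samples is taken, since the shift table does not correct for that.
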